4.3.4.5. PASI score

The descriptive statistics of PASI total score, change from baseline and percent improvement from baseline will be presented by scheduled visit.

4.3.4.6. DLQI

The following by scheduled visit analyses will be performed for DLQI score.

- The descriptive statistics of the observed value and change from baseline
- The number and proportion of participants who achieved DLQI score of 0 or 1 with $DLQI > 1$ at baseline

4.3.4.7. EQ-5D

The observed value and change from baseline will be summarized using descriptive statistics for EQ-5D VAS score by scheduled visit. In addition, the domain score (5-point Likert response scale 0 - 4) will be summarized using descriptive statistics by scheduled time points separately.

4.4. Exploratory Analysis

Data will be summarized based on FAS and those will be presented by diagnosed disease (GPP or EP) unless specified.

4.4.1. Definition of Endpoints

4.4.1.1. Children's Dermatology Life Quality Index (CDLQI)

The CDLQI is an adapted version of the DLQI for the pediatric population and will be utilized in the adolescent population in this study. The adaption and validation of the CDLQI was undertaken

by the original developer of the DLQI to ensure it addressed the specific needs of the pediatric population. The CDLQI is a 10-item instrument that has 4 item response options and a recall period of 1 week. Higher scores indicate greater impact on HRQoL. The instrument is designed for use in children, is self-explanatory and can be simply handed to the participant who is asked to fill it in with the help of the child's parent or caregiver (provided in the study manual).

4.4.1.2. JDA severity index score

JDA severity index score contains 2 components: skin symptoms, systemic symptoms/laboratory findings. The additional definitions are described in 4.3.4.2.

4.4.2. Analysis Methods

4.4.2.1. CDLQI

CDLQI will be summarized as same way of DLQI.

4.4.2.2. JDA severity index score

The observed values and change from baseline for the 2 components of JDA severity index score will be presented by scheduled visit only for the participants with GPP.

4.5. Safety Analyses

The safety data will be summarized based on SAS and it will be presented by diagnosed disease (GPP or EP), and 'GPP+EP' column that combines GPP and EP will also be presented.

For all continuous safety variables, descriptive statistics will include the N, mean, standard deviation, median, minimum, and maximum. Categorical variables will be summarized by using frequency counts and percentages.

4.5.1. Extent of Exposure

For the following parameters, descriptive statistics will be presented of continuous variables and categorial variables frequency counts and percentages will be presented.

- Treatment duration (weeks)
 - (date of last dose of study intervention – date of first dose of study intervention + 1 day) /7.
- Average daily dose
 - (tablets dispensed – tables retuned) x tablet strength /(date of last dose of study intervention – date of first dose of study intervention + 1 day).

Study intervention compliance will also be summarized descriptively. See [Appendix 7](#) for further details.

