## Description of Interventions

Intervention Name	JNJ-77242113
Intervention Description	film-coated tablet containing 200 mg JNJ-77242113
Type	Drug
Dose Formulation	Tablet
Unit Dose Strength	200 mg per tablet
Dosage Level	1×200 mg tablet once daily
Route of Administration	Oral
Use	Experimental
Investigational Medicinal Product (IMP)	Yes
Non-Investigational Medicinal Product/Auxiliary Medicinal Product (NIMP/AxMP)	No
Sourcing	Provided centrally by the sponsor
Packaging and Labeling (Labels will contain information to meet the applicable regulatory requirements)	Study intervention will be provided in blister packs. Each pack will be labeled as required per local requirements.  The blisters are packaged in child resistant Dosepaks.
Delivery Instructions	Swallow tablet whole. Given with 240 mL water. The tablet should not be broken or crushed.
Fasting Requirement	At least 2 hours before taking the study intervention and for at least 30 minutes after taking the study intervention.
Current/Former Names or Aliases	JNJ-77242113 and previously referred to as aPi2915, PN21235, PN-21235, and PN-235.

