#### **6.5. Study Intervention Compliance**

Participant compliance with study intervention will be assessed at each visit during the treatment period by counting returned tablets.

Each participant's overall compliance with study intervention since the first dose of study intervention will be assessed by the site at each visit. A participant will be considered noncompliant with the study intervention if they take less than 80% or greater than 120% of the expected tablets during participation in this study, unless study intervention is withheld for safety reasons. Protocol deviations for compliance will be assessed at Week 16, 24, and 52 or the Early Termination (ET) Visit, if performed before Week 52.

If a participant's study intervention intake is not according to the protocol, the investigator will take the necessary measures to ensure future adherence to the protocol. If necessary, the participant may be discontinued from study intervention by the investigator or medical monitor (Section 7).

Study intervention compliance will be further detailed in the SAP.

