#### **6.8. Treatment of Overdose**

For this study, any dose of JNJ-77242113 greater than 200 mg in a single day will be considered an overdose. The sponsor does not recommend specific treatment for an overdose.

Decisions regarding dose interruptions will be made by the investigator in consultation with the medical monitor based on the clinical evaluation of the participant.

In the event of an overdose, the investigator or treating physician should:

- Contact the medical monitor immediately.
- Closely monitor the participant for AE/SAE and laboratory abnormalities.
- Document the quantity of the excess dose as well as the duration of the overdosing in the source documents.
- Evaluate the participant to determine, in consultation with the medical monitor, whether study intervention must be interrupted.

- Obtain a plasma sample for PK analysis if requested by the medical monitor (determined on a case-by-case basis).

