1.2. Study Design

This is a Phase 3, open-label, multicenter study to evaluate the efficacy and safety of JNJ-77242113 for the treatment of participants with generalized pustular psoriasis (GPP) or erythrodermic psoriasis (EP).

A target of 16 (GPP, n=8; EP, n=8) participants will be enrolled in this study. All participants will take JNJ-77242113 from Week 0.

The total duration of this study for each participant is approximately 165 weeks, which includes: a ~5-week screening period, a 52-week treatment period, a 104-week long term extension treatment period (LTE), and a 4-week safety follow-up period.

All the participants will receive JNJ-77242113 200 mg once daily for 52 weeks. Participants completing Week 52 visit may be eligible to enroll in the LTE. The LTE will begin at the end of Week 52 and will continue until Week 156. All the participants will have a 4-week safety follow up period at the end of the treatment period or after the last dose of study intervention.

Efficacy, safety, PK, immunogenicity, and biomarkers will be assessed according to the Schedule of Activities in protocol Section 1.3. In addition, there will be 2 optional substudies for participants who provide consent. Sample collections for these substudies include a pharmacogenomic blood sample and photograph collection.

The first database lock (DBL) will occur when all participants complete Week 24 of the study. Additional DBLs may occur after Week 24 to support regulatory submissions and scientific disclosures.

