6.6. Appendix 6 Intervention Compliance

Treatment compliance will be assessed based on FAS. Compliance will be summarized descriptively (N, mean, standard deviation, median, and range). Overall compliance will be categorized as > 120%, >100 to \leq 120%, 80 to \leq 100%, and < 80%.

Compliance will be calculated as follows:

Compliance (%)=(actual number of tablets taken/total number of tablets supposed to be taken)
x100.

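### The average daily dose formula in SAP 4.5.1 counts unreturned tablets as taken, so it overstates dose for participants still on treatment at a database lock

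*SAP*

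**What the plan says.** SAP 4.5.1 defines average daily dose as tablets dispensed minus tablets returned, "x tablet strength /(date of last dose of study intervention"; the denominator then subtracts the first dose date and adds one day. Treatment duration in the same section uses the same day count, "date of last dose of study intervention – date of first dose of study intervention + 1 day) /7". The SAP version history shows that version 2 removed cumulative dose and added average daily dose.

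The regimen in the protocol's Description of Interventions is "1×200 mg tablet once daily". On timing, SAP 1.2 says "The first database lock (DBL) will occur when all participants complete Week 24 of the study", with further locks possible. Treatment runs to Week 52 and, in the extension, to Week 156.

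The Schedule of Activities (protocol 1.3) makes Week 24 a dispensing visit. Its footnotes put dispensing after all other procedures and also allow it between visits. Protocol 6.2 asks participants to bring back all containers, empty or not, and protocol 6.5 has the site count returned tablets at each visit.

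The SAP has no rule for supply still open at a lock, no data cut-off convention, and no definition of last dose date for someone still taking the drug. SAP 6.6 defines compliance from "actual number of tablets taken/total number of tablets supposed to be taken" and does not say how the tablets taken are counted.

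**The concern.** Dispensed minus returned equals tablets taken only when every dispensed tablet has been either swallowed or brought back. At the Week 24 lock that is not the expected state. Participants leave the visit with new supply that can be returned only at a later visit. Those tablets enter the numerator with no matching return and, depending on the last dose date, with few or no matching days.

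The result is a biased exposure figure in a table where it will be seen. Each disease group has a target of 8 participants, and SAP 4.5 reports minimum and maximum. Average daily dose is the only dose-quantity summary left in SAP 4.5.1 since cumulative dose was removed. The bias is always upward, so it also hides missed doses.

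**Working it through.** **Inputs**
- Strength and regimen: 200 mg, one tablet daily (protocol, Description of Interventions).
- Dispensing visits: Weeks 24, 28, 32, 36, 44, then 52 for extension entrants, then each extension visit from Week 64 through Week 148 (protocol 1.3).
- Tablets per dispensing: not stated. Assumption: exactly enough to reach the next scheduled visit, so 28 tablets at Week 24, 56 at Week 36 and 84 at Week 52.
- Last dose date for an ongoing participant: not stated. It is varied below.
- Elapsed days at Week 24: 24 × 7 = 168.

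**Formula.** For a fully adherent participant with T tablets taken over T days and H tablets in hand, the SAP formula gives 200 × (T + H)/T = 200 × (1 + H/T).

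**Reproducing the planned dose.** With treatment finished and every unused tablet returned, H = 0 and the result is 200 mg/day, as intended.

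**Week 24 lock, full adherence, 28 tablets just dispensed**

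| Last dose date used | Calculation | mg/day |
|---|---|---|
| Week 24 visit | (168 + 28) × 200/168 | 233.3 (116.7% of plan) |
| Midway to Week 28 | 196 × 200/182 | 215.4 |
| Supply exactly used up | 196 × 200/196 | 200.0 |

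Counting the visit day itself as day 169 changes the first row only to 196 × 200/169 = 232.0. If each supply carried four extra tablets, the first row would be (168 + 28 + 4) × 200/168 = 238.1.

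**Masking of under-dosing at Week 24** (last dose at the visit, missed tablets returned). A participant who took 90% of tablets truly averaged 180 mg/day, but the formula gives (0.9 × 168 + 28) × 200/168 = 213.3. A participant who took 140 of 168 tablets (83.3%) would show (140 + 28) × 200/168 = 200.0, which looks like perfect adherence.

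**Later visits, if a lock happened to date last dose there**
- Week 36: (252 + 56) × 200/252 = 244.4 mg/day (122.2%).
- Week 52, extension entrant: (364 + 84) × 200/364 = 246.2 mg/day (123.1%).
- Week 148: (1,036 + 56) × 200/1,036 = 210.8 mg/day.

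**Checking the repair at Week 24.** Counting only reconciled supply, and ending the day count at the last dose it covers, gives 168 × 200/168 = 200.0. Dropping the open supply from the numerator but running the days midway to Week 28 gives 168 × 200/182 = 184.6. Both parts therefore have to change together.

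**The case against.** The strongest defence is that SAP 4.5.1 is a one-line definition and that site accountability is done visit by visit. A programmer might naturally count only reconciled supply over matching dates and get 200 mg/day. That may happen, but the text does not say so. Applied as written, the formula includes the open supply, and neither SAP 6.6 nor the list of changes to protocol-planned analyses in SAP 4.8 corrects it.

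Other parts of the defence stand:
- **Size.** The magnitudes rest on assumed supply quantities and an assumed last dose date. Early enrollees will be past Week 24 when the last participant reaches it. If data run to the lock, 233 mg/day would not apply to everyone.
- **Later locks.** A reader might infer that every later lock is affected. A final lock with nobody on treatment and all tablets returned gives 200 mg/day. No lock is fixed at Week 36 or Week 52, so those figures are illustrations.
- **Noncompliance.** A reader might infer that adherent participants will be classed as noncompliant under protocol 6.5, whose limits are "less than 80% or greater than 120% of the expected tablets". The documents do not support that. SAP 6.6 refers to tablets actually taken, and protocol 6.1 requires administration to be recorded in source documents and the CRF, so another data source exists. The effect arises only if tablets taken is also derived as dispensed minus returned, and even then 116.7% at Week 24 stays below 120%.
- **Overdose.** A reader might infer false overdose signals, because protocol 6.8 says "any dose of JNJ-77242113 greater than 200 mg in a single day will be considered an overdose". That definition applies to a single day and is acted on by the investigator. A period average in an exposure table does not feed that process.

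**Conclusion.** The point holds. At the Week 24 lock, and at any later lock with participants still on treatment, the SAP 4.5.1 formula overstates average daily dose for anyone holding tablets beyond those needed up to the last dose date used. The direction follows from the formula alone.

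The size does not. Under full adherence and supply to the next scheduled visit, the Week 24 value lies between 200 and about 233 mg/day depending on the last dose date convention, against a true 200.

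The consequence is limited to a descriptive exposure summary. No formal testing is planned (SAP 2), and the primary endpoint and treatment duration do not use tablet counts. The change is worth making because a stated rule gives a wrong number at the first planned lock and the repair is small.

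**What to change.** Amend SAP 4.5.1 so that numerator and denominator cover the same interval for every participant, on or off treatment:

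1. Count only supplies with a recorded return by the data cut-off. An empty pack brought back counts as a return of zero tablets.
2. End the day count at the last dose covered by those supplies.
3. Exclude open or never-returned kits, and the days they cover, from both parts, and list them. Running the denominator to last dose for an off-treatment participant whose final kit never came back would bias the value downward.
4. Define last dose date for participants still on treatment at a lock; treatment duration needs this too.
5. State in SAP 6.6 that compliance uses the same reconciled tablet count and interval.

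The cross-reference in SAP 4.5.1 can be corrected at the same time: it sends the reader to Appendix 7 (laboratory grading) for compliance, which is in Appendix 6.

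The cost is a few sentences and minor programming. The most recent unreconciled interval drops out of the summary, which the kit listing makes visible.

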4.5.2. Adverse Events

The verbatim terms used in the CRF by investigators to identify adverse events will be coded using MedDRA. In general, any AE occurring at or after the initial administration of study intervention up to 4 weeks after the last dose or treatment discontinuation is considered to be treatment emergent. If the event occurs on the day of the initial administration of study intervention, and either event time or time of administration are missing, then the event will be assumed to be treatment emergent. If the event date is recorded as partial or completely missing, then the event will be considered to be treatment emergent unless it is known to be prior to the first administration of study intervention based on partial onset date or resolution date. All reported treatment-emergent adverse events will be included in the analysis. For each adverse event, the number and percentage of participants who experience at least 1 occurrence of the given event will be summarized.

Summary tables will be provided for treatment-emergent adverse events:

- AEs
- AEs with frequency of at least 2 participants in ‘GPP+EP’ column
- SAEs
- AEs leading to discontinuation of study intervention
- AEs by severity
- AEs by relationship to study intervention
- SAEs by relationship to study intervention
- AEs by study period

In addition to the summary tables, listings will be provided for treatment-emergent adverse events:

- AEs
- SAEs
- AEs leading to death
- AEs leading to discontinuation of study intervention
- AEs for psoriasis
- Suicidal ideation or suicidal behavior
- Had hypersensitivity including anaphylactic reactions

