- j. For W16 and W52: Height will be measured only for participants  $< 18$  years on the first date of Screening.
- k. Vital signs will include temperature, pulse/heart rate, respiratory rate, and blood pressure.
- l. A 12-lead ECG will be performed locally. Participants should rest in a supine position for at least 5 minutes before ECG recording and should refrain from talking or moving arms or legs.
- m. PHQ-9 and C-SSRS will be completed after PROs and before all other study procedures.
- n. If TB is suspected at any time during the study, a chest radiograph or chest CT, and QuantiFERON-TB® or T-SPOT® test should be performed.
- o. A negative urine test result is required at each visit prior to dispensing study intervention. A urine pregnancy test may be performed at any time during the visit, including before PRO collection.
- p. At Week 0, all blood samples should be collected prior to study intervention administration, and the date and time of collection should be recorded as instructed in the Laboratory Manual. At all other study visits where applicable, the date and time of the dose prior to the PK sample should be recorded as instructed in the CRF completion guidelines.
- q. Fasting requirement for lipid panel:  $\geq 6$  h unless medically contraindicated.

- r. Urinalysis may be performed any time during the study visit including before PRO collection.
- s. Collect 1 trough and 1 peak sample at Week 4 and Week 16. Details to be specified during training. If peak/trough collection at the Week 4 and Week 16 visits is not feasible, collection at an alternative visit is allowed.
- t. All medications taken and new or worsening AEs reported after signing the ICF will be recorded. See CRF completion guidelines.

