### Adverse Events

The verbatim terms used in the CRF by investigators to identify AEs will be coded using the Medical Dictionary for Regulatory Activities (MedDRA). Any AE occurring at or after the initial administration of study intervention or that is a consequence of a pre-existing condition that has worsened since baseline is considered to be treatment-emergent. All reported treatment-emergent AEs will be included in the analysis. For each AE, the percentage of participants who experience at least 1 occurrence of the given event will be summarized.

The following analyses will also be used to assess the safety of participants in the study:

- The incidence and type of AEs.
- The incidence and type of SAEs.
- The incidence and type of AESIs.
- The incidence and type of severe AEs.
- The incidence and type of treatment-related AEs and SAEs as assessed by the investigator.
- The incidence and type of AEs leading to discontinuation of study intervention.

Listings of participants with SAEs, severe AEs, AEs of psoriasis, AESIs, and AEs leading to discontinuation of study intervention will also be provided. Summaries, listings, datasets, or participant narratives may be provided, as appropriate, for those participants who die, who discontinue intervention due to an AE, or who experience a severe or an SAE.

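### SAP 4.5.2 omits the protocol's worsening clause from the definition of treatment-emergent AEs, and SAP 4.8 does not declare the change

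*SAP*

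**What the plan says.** Protocol 9.3.5 (Adverse Events) gives two alternative routes to treatment-emergent status. The first is timing: "Any AE occurring at or after the initial administration of study intervention". The second is worsening: "or that is a consequence of a pre-existing condition that has worsened since baseline is considered to be treatment-emergent".

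SAP 4.5.2 opens with the words in general and then gives timing only: "any AE occurring at or after the initial administration of study intervention", bounded above by "up to 4 weeks after the last dose or treatment discontinuation is considered to be treatment emergent". Its remaining rules cover events on the day of first dose and events with partial or missing dates. These also turn on timing. An event with an incomplete date counts as treatment-emergent "unless it is known to be prior to the first administration of study intervention based on partial onset date or resolution date". No rule covers an AE that starts before first dose and becomes worse afterwards.

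The outputs follow the definition. SAP 4.5.2 states that "Summary tables will be provided for treatment-emergent adverse events" and names eight of them. It then limits its seven listings in the same way, including those for SAEs and for AEs of psoriasis.

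SAP 4.8 records two departures from the protocol's planned analyses, on laboratory abnormalities and on physical examination findings. The treatment-emergent definition is not there. The SAP version history presents the wording of 4.5.2 as a clarification.

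**The concern.** The frequency and type of AEs and SAEs is a secondary endpoint in both documents, so the rule for which events count is part of that endpoint's definition. The protocol would count an AE that began before dosing and worsened on drug. The SAP, read as written, need not.

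Such events can exist. Protocol 8.4.1 collects AEs from signature of the consent form, and screening lasts about 5 weeks and can be extended. Some washouts end inside that window: under the exclusion criteria, topical treatments stop 2 weeks before first dose, and phototherapy and systemic immunomodulators 4 weeks before.

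At stake is whether a small single-arm study reports every event that its protocol calls treatment-emergent, and whether a reader of the SAP can tell that a protocol clause is no longer applied.

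**Working it through.** There is no sample-size, power or error-rate figure to reproduce; Protocol 9.5 sets the sample size by feasibility. The check compares the texts, follows one case through both rules, and sizes the effect.

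**1. The two definitions**
- Onset at or after first dose: counted by the protocol and by the SAP.
- Upper limit of 4 weeks after dosing ends: in the SAP definition only. It matches the protocol's AE collection period and is not at issue here.
- Pre-existing condition that worsens after baseline: counted by the protocol, not mentioned by the SAP.
- Change logged in SAP 4.8: no.

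**2. Which events are exposed**
- A condition that was only medical history at consent and worsens on drug has no earlier AE record. Its worsening would be entered as an AE after first dose, and the SAP's timing rule counts it.
- The gap is therefore confined to conditions already recorded as AEs between consent and first dose.

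**3. One case under both rules**

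Take an AE that starts as mild during screening and becomes severe after first dose.
- *Worsening entered as a new record dated when it occurred.* Protocol: counted. SAP: counted. Difference: none.
- *Original record kept, with its pre-dose onset date and an updated severity.* Protocol: counted, by the worsening route. SAP: not counted by the timing rule, so absent from the eight tables and seven listings of 4.5.2.

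The documents do not say which recording rule applies. The Schedule of Activities footnote says "All medications taken and new or worsening AEs reported after signing the ICF will be recorded" and then refers to the CRF completion guidelines, which are not among the documents.

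**4. Size of one omission**

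Inputs: 8 participants with GPP, 8 with EP, 16 in all (Protocol 4.1, SAP 1.2).
- By-disease column, one given term: 1/8 = 12.5 percentage points.
- Combined GPP+EP column, one given term: 1/16 = 6.25 percentage points.
- Table of AEs in at least 2 participants: a term seen in 2 participants falls to 2 − 1 = 1 and leaves the table.
- Overall AE or SAE incidence: the same 12.5 or 6.25 points if the participant has no other qualifying event, and 0 if there is one. For AEs, another event is likely. Protocol 2.2 reports that 52.4% of participants on active drug had at least one AE in the 16-week Phase 2b study, and treatment here can run to 52 + 104 = 156 weeks.

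**The case against.** The strongest reply is that the omitted clause is redundant. Protocol Appendix 3 (10.3.1) already makes aggravation from the baseline condition an AE, and SAP 4.1.2 sets the safety baseline just before first dose. Worsening after baseline is then itself an AE occurring after first dose, which the SAP sentence covers. The SAP's operative sentence also speaks of an AE occurring; onset date appears only in the rule for incomplete dates. This makes loss of events less likely, but it does not settle the matter. Neither text says that a worsening screening AE receives a new record with a post-dose date. The protocol also carries the worsening clause alongside that same AE definition, so its own text does not treat the clause as superfluous. The words in general leave latitude but give a programmer no rule.

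Three stronger readings are tempting, and the documents do not support them.

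- *That such an event would disappear from all safety reporting.* The limit applies to the outputs of SAP 4.5.2. The AESI listing in 4.5.2.1 is not expressly restricted to treatment-emergent events. SAP Appendix 1 lists deaths and discontinuations separately. The laboratory grade, PHQ-9 and C-SSRS outputs do not depend on the AE start date. Expedited SAE reporting under Protocol 8.4.1 is unaffected.
- *That a disease flare which becomes serious on drug is the event most likely to be lost.* Appendix 3 (10.3.5) requires hospitalizations during participation to be reported as SAEs, apart from planned ones, which points to a fresh report on escalation. Protocol 6.9 discourages changing effective therapy for the explicit purpose of study entry, and eligibility is rechecked before first dose. Disease worsening would also show in the by-visit efficacy scores, although these do not replace AE reporting.
- *That every affected participant shifts overall AE incidence by 12.5 points.* As shown above, that holds for a given term, or for a participant with no other qualifying event.

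**Conclusion.** The point holds as an undeclared departure of the SAP from the protocol on how a secondary safety endpoint is counted. That much rests on the text alone.

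Whether any event is lost is conditional. It requires an AE with onset between consent and first dose, worsening after first dose, and a CRF practice that keeps one record with the pre-dose onset date. If worsening is always a new record, the effect is zero. The number of participants affected cannot be derived from the documents and may be none. A reader might infer that events will be lost; the documents support only that they could be. The group sizes make each such case visible at term level, and the correction is cheap, so the sponsor should make it, ideally before the first database lock at Week 24.

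**What to change.** Restore the protocol's worsening clause in SAP 4.5.2 and state how worsening is identified in the data. Either of two rules would serve:
- a new AE record dated at the worsening, with a reference to the CRF guideline that requires it; or
- an increase in severity or seriousness after first dose on a record that began earlier.

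If leaving the clause out is intended, enter it in SAP 4.8 with the reason.

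A listing of all AEs, including those with onset before first dose, would be a useful addition in a study of 16 and would close the gap whichever recording practice applies.

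The main change costs one sentence in the SAP and one programming flag.
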